## **1.3.** Statistical Hypotheses for Trial Objectives

The primary hypothesis of the open label safety phase of this study is that the novel subretinal Delivery System is sufficiently safe and usable to deliver cells to the subretinal space. An additional hypothesis is that Palucorcel is safe and well tolerated when delivered as a single dose to the subretinal space.

### 1.4. Sample Size Justification

The sample size of 21 subjects is based on the number of subjects require to allow for an adequate clinical assessment of the safety and usability of the novel Delivery System.

### 1.5. Randomization and Masking

Not applicable, because the study only enrolled the initial open-label safety cohort.

### 2. GENERAL ANALYSIS DEFINITIONS

Analyses will be conducted using SAS Version 9.2 or higher. Continuous variables, including numerical variables assessed on a discrete scale, will be analyzed using descriptive statistics, including number of subjects, mean, median, standard deviation, maximum, and minimum. Minimum and maximum will be reported using the same decimal precision as the corresponding raw data, mean and median will be reported using one more decimal digit than the raw data. Standard deviation will be reported using two more decimal digits than the raw data. For categorical variables, analyses will include counts of subjects and percentages. The treated eye is the eye designated for treatment. The fellow eye is the other eye. Where applicable, results will be summarized by "Treated Eye" or "Fellow Eye" or "Both Eyes", not left or right eye.

# 2.1. Study Day

Study Day will be computed relative to the Surgery Date, where the Surgery Date is Day 1. Study Day will be defined as follows:

- (Key Date Surgery Date + 1), if Key Date is equal or greater than the Surgery Date;
- (Key Date Surgery Date), if Key Date is prior to Surgery Date;

where Key Date can be a date of assessment, onset of an adverse event, or start of concomitant medication.

## 2.2. Baseline

For all assessments except for BCVA measurements (i.e., logMAR and total letters correct, both standard and low luminance), baseline will be defined as the most recent value prior to the Surgery Date (and time, if applicable). Thus the baseline could be derived based on Screening or Day 1 pre-op assessments or unscheduled pre-op assessments where applicable.

Baseline BCVA is assessed at an optional pre-screening visit (not recorded on the electronic case report form [eCRF] thus not used for analysis) and at the regular Screening visit (twice at that visit). For BCVA logMAR and total letters correct (both standard and low luminance), the better score at these 2 assessments will be used for baseline. For BCVA logMAR, a lower score is better. For total letters correct, a higher value is better.

Re-screening is allowed per protocol and the subject is not necessarily required to repeat every test during the 2nd screening. When a subject is re-screened, he/she receives a new subject ID. If a baseline value is not present for the current subject ID for this type of subject, it will be necessary to use the screening/baseline value captured in the 1st screening visit for that subject (captured using their previous subject ID) as the baseline value.

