PGIC-Q								x	x	
CGIC								x	x	
Change in concomitant medications				<-----	Continuous----->					
Adverse events				<-----	Continuous----->					
Blood samples volume ⁱ		16.3 mL	0	0	20 mL ^k	16.3mL	10 mL	10 mL	10 mL	16.3 mL

BCVA=Best Corrected Visual Acuity; CGIC=Clinician Global Impression of Change; ETDRS=Early Treatment Diabetic Retinopathy Study; IOP=intraocular pressure; MN Read=Minnesota reading test; NEI-VFQ-25=National Eye Institute Visual Functioning Questionnaire; PGIC-Q=Patient Global Impression of Change – Quality of Life; PGIC-S=Patient Global Impression of Change – Symptoms; SD-OCT=spectral domain optical coherence tomography; SF-36=Short Form (36) Health Survey, FRI= Functional Reading Index questionnaire

Note 1: Screening procedures must occur within 45 days prior to treatment and may occur over multiple days. An additional optional pre-screening visit may be performed to determine potential subject BCVA for eligibility purposes. At the next screening visits, BCVA will be performed twice and the best value (lowest logMAR value) will be used as the subjects' baseline BCVA value.

Note 2: If a subject withdraws early from the Safety Run-in Phase, the end-of-study assessments (described in [Table 2](#)) should be performed.

- a) Subjects will be presented with an optional pre-screening ICF to allow the determination of their BCVA results prior to full study screening. The subjects who meet the BCVA eligibility criteria will be further screened to determine the full study eligibility. For the full study eligibility assessments, the subject will be presented a separate ICF within 45 days prior to treatment. The pre-screening visit is optional
- b) Best Corrected Visual Acuity testing includes BCVA using the ETDRS chart under high illumination and standardized conditions at 4 meters and 1 meter (as needed).
- c) Axial length should be recorded once at screening as a baseline measure. Any instrument may be used OR measurement taken from the subjects medical records may be utilized. Measurement, instrument and date of recording will be noted in the CRF.

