9.2.2. Endpoints

Primary Endpoints

The endpoints of the open-label Safety Run-in Phase are all related to the objective of evaluating the safety profile of the procedure, Delivery System, and of the implanted hUTC cells.

Major Secondary Endpoints

- Proportion of subjects losing ≥ 15 BCVA letters from baseline at 12 months following treatment with CNTO 2476
- Change in mean number of BCVA letters from baseline at the 6- and 12-month visits following treatment with CNTO 2476
- Growth rate of GA lesion documented at baseline to 6 and 12 months following treatment with CNTO 2476. The area of GA is determined based primarily on fundus autofluorescence as well as fluorescein angiography and fundus photos

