- Significant loss of vision: defined as a decrease of ≥ 15 BCVA letters from baseline in the treated eye at the Week 4 visit. Unscheduled BCVA assessments after surgery prior to the Week 4 visit and assessments after Week 4 will not be considered here.

The Events of Special Interest will be summarized for the Safety Cohort. For each event, the count and percentage of subjects who had the event and the Exact Binomial 95% CI will be presented. Individual subject events will be presented in a data listing.

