## 6. EFFICACY

## 6.1. BCVA

The primary efficacy measure will be the BCVA testing performed after refraction and under standardized photopic lighting conditions and distance using an ETDRS logMAR chart.

If the BCVA assessment was done, but total letters correct is missing because neither the 4m nor the 1m assessments could be done, (i.e., only highest degree of vision was done), the BCVA total letters correct will be assigned a value of 0 and BCVA logMAR score will be assigned a value of 1.7 (using the formula logMAR = 1.7 - [0.02 x total letters correct]).

Descriptive statistics will be presented for BCVA (letters and logMAR) at baseline and at each scheduled follow-up time point, and for the change from baseline, for the treated and fellow eye.

The count and percentage of BCVA responders at each follow-up time point (responder=yes for subjects who have BCVA change from baseline >=15 letters) will be summarized for the treated and fellow eye.

BCVA data for individual subjects will be presented in a data listing.

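### The SAP plans no summary of ≥15-letter BCVA loss at Month 12, a protocol major secondary endpoint, although it tabulates ≥15-letter gain at every follow-up visit

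*SAP*

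**What the plan says.** Protocol 9.2.2 lists three major secondary endpoints. The first is the proportion of subjects losing 15 or more "BCVA letters from baseline at 12 months following treatment with CNTO 2476". The synopsis repeats it among the secondary efficacy endpoints. Both are current text under Amendment 3.

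The SAP deals with 15-letter changes in two places.

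- **SAP 5.3 (Events of Special Interest).** Significant loss of vision is a fall of at least 15 "BCVA letters from baseline in the treated eye at the Week 4 visit". For this event, "assessments after Week 4 will not be considered here". The display is fixed: "the count and percentage of subjects who had the event and the Exact Binomial 95% CI will be presented".
- **SAP 6.1 (BCVA).** Besides descriptive statistics for BCVA and its change at each scheduled visit, the only categorical display is "The count and percentage of BCVA responders at each follow-up time point", for treated and fellow eyes. A responder has a change of at least 15 letters, and the protocol synopsis defines response as an increase. The section ends: "BCVA data for individual subjects will be presented in a data listing".

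The baseline for all of these is set in SAP 2.2: "For BCVA logMAR and total letters correct (both standard and low luminance), the better score at these 2 assessments will be used for baseline". Protocol Table 1, Note 1 has the same rule: "BCVA will be performed twice and the best value (lowest logMAR value) will be used".

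**The concern.** An endpoint that the protocol names should have a planned summary in the SAP. This one has none under any baseline definition. A programmer who follows the SAP as written would deliver a gain table at every visit, a loss count at Week 4 and nothing on loss at Month 12.

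The omission is one-sided. Protocol 3.2.1 provides no control group, so the gain and loss proportions will be read largely at face value. Protocol 3.2.4 justifies BCVA as a measure because it captures both benefit and harm. After Week 4 the planned categorical tables capture only benefit. A mean change near zero, or above it, can hide a substantial group of eyes that lost vision.

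**Working it through.** **1. Endpoints against planned summaries.**

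| Protocol 9.2.2 major secondary endpoint | Planned SAP summary |
|---|---|
| Proportion losing ≥15 letters at 12 months | None. SAP 5.3 covers Week 4 only; SAP 6.1 covers gain only |
| Change in mean letters at 6 and 12 months | SAP 6.1, change from baseline at each visit |
| Growth rate of the GA lesion to 6 and 12 months | SAP 6.2, change in GA area and yearly rate |

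Only the first row is empty. The 15-letter gain that SAP 6.1 does tabulate is not among the endpoints that 9.2.2 now lists.

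**2. Visits.** Protocol Table 1 schedules post-operative BCVA at Week 4 and Months 2, 3, 6 and 12 (five visits). Table 2 adds Months 18, 24, 30 and 36 (four visits). Gain is counted at 5 + 4 = 9 visits in both eyes. Loss is counted at one visit, in the treated eye.

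**3. What the planned display would show on known data.** Protocol 1.1.2.2 gives the predecessor study's 12-month results in 26 subjects, using changes of 3 lines or more:

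| | Treated eye | Fellow eye |
|---|---|---|
| Gain | 10/26 = 38.5% | 1/26 = 3.8% |
| Loss | 6/26 = 23.1% | 3/26 = 11.5% |

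The treated-eye median moved from logMAR 1.2 to 1.1, an improvement. Under this SAP the gain row and the improved median would be tabulated, and the loss row would not. The protocol itself reports both rows for the predecessor, at 6 and at 12 months.

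**4. Size in this study.** SAP 2.5 sets the Safety Cohort at 21, so one subject is 1/21 = 4.8%. If the predecessor rate held, and 3 lines are taken as 15 letters, the expected number is 21 × 6/26 = 4.8 losses. That is an illustration, because the predecessor used another delivery system and its baseline rule is not given. Exact binomial 95% intervals with all 21 assessed:

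| Losses | Percentage | Exact 95% CI |
|---|---|---|
| 0/21 | 0% | 0–16.1% |
| 1/21 | 4.8% | 0.1–23.8% |
| 4/21 | 19.0% | 5.4–41.9% |
| 5/21 | 23.8% | 8.2–47.2% |

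**5. Eyes that cannot show the event.** SAP 6.1 gives logMAR = 1.7 − 0.02 × letters, so letters = (1.7 − logMAR)/0.02. The eligible range 0.6 to 1.6 is (1.7 − 0.6)/0.02 = 55 letters down to (1.7 − 1.6)/0.02 = 5 letters. LogMAR 1.4 is 15 letters. The lowest assigned score is 0, so an eye that starts below 15 letters (logMAR above 1.4) cannot register a 15-letter loss. It stays in the denominator and lowers the proportion.

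**6. The baseline rule.** With screening scores a and b, the better score exceeds their mean by max(a,b) − (a+b)/2 = |a−b|/2, which is never negative. Compared with a mean baseline, the rule can only keep or raise loss counts and keep or lower gain counts. Enumerating 520,251 combinations of two screening scores and one follow-up score (0 to 100 letters) found no exception.

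**The case against.** **The information is not lost.** This stands in part. SAP 6.1 summarises change from baseline at each visit, SAP 2 includes the minimum among the descriptive statistics, and individual values are listed. SAP 5.1 also splits ocular adverse events at the Week 4 visit, so a late fall in vision may appear there if it is reported as an event. A reader could count the losses by hand. That is still no planned summary of a named endpoint. A reader might infer that late loss is excluded from the study altogether, but the Week 4 restriction applies only to the event of special interest.

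**The protocol leaves the BCVA summaries to the SAP, and nothing is tested.** Protocol 11.3 does refer to the SAP for the descriptive statistics, and no decision depends on this proportion. That keeps the matter small. It does not remove the endpoint from 9.2.2. SAP 9 shows the contrast: it gives a reason for leaving out the patient-reported outcomes, and no such reason is given here.

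**The responder definition says only change, so it might cover losses.** It does not. The protocol synopsis defines response as an increase.

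**A stronger reading: the baseline itself is wrong.** From step 6 a reader might infer that the better-of-two rule biases BCVA change downward and should give way to the mean. The documents do not support that.

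- The rule is prespecified and identical in both documents, and it fits protocol 9.1.1, which describes BCVA as the best achievable vision.
- Step 6 compares two baselines; it says nothing about bias against the true change. Protocol 4.1 treats the eye with the worse screening BCVA. That selection favours eyes that scored low by chance and pushes later change upward. A mean baseline would keep this upward push without the offset.
- No test-retest SD is given, and the testing protocol for follow-up visits is not available. If follow-up also took the better of two tests, the asymmetry would largely cancel.

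**Conclusion.** The point holds as a gap between protocol and SAP. Protocol 9.2.2 names 15-letter loss at 12 months, SAP 5.3 and 6.1 between them do not summarise it, and the categorical BCVA tables after Week 4 show gains only. This follows from the text and needs no assumption.

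Its weight is modest. The study is descriptive with 21 subjects, and the count can be recovered from the listing. What is missing could still matter to a reader: about five treated eyes in 21 if the predecessor's 23% applied, with an exact interval of roughly 8% to 47% around 5/21. Those figures assume that the predecessor rate carries over, that 3 lines equal 15 letters, and that all 21 subjects are assessed at Month 12.

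The better-of-two baseline is not a defect, and a mean-baseline table is optional.

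**What to change.** Add to SAP 6.1 the count and percentage of subjects losing at least 15 letters from the protocol-defined baseline at Month 12, for treated and fellow eyes, with the exact binomial 95% CI already used in SAP 5.3. Preferably give it at each scheduled visit, beside the responder table, so that gains and losses are read together.

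Footnote the number of eyes with a baseline below 15 letters (logMAR above 1.4 by the SAP formula), because they cannot register the event.

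Leave SAP 2.2 and the Week 4 event in SAP 5.3 as they are.

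The cost is one or two SAP sentences and one descriptive row per visit, from data already collected and already used for the responder table. Eligibility, visits and study conduct do not change. The intervals will be wide, and the fellow eye is not a clean control because the eye with the worse screening BCVA is the one treated.

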### 2.3. Visit Windows

All "by-visit" analyses will be presented by scheduled study visit as recorded on the eCRF; no visit windows will be used. Unscheduled assessments will be presented in by-subject data listings.

## 2.4. Pooling Algorithm for Analysis Centers

Not applicable. Data from all investigative sites (centers) will be combined together for analysis irrespective of the site in which the subject undergoes evaluations.

## 2.5. Analysis Sets

The initial Safety Cohort is defined as the first 21 subjects enrolled in the Open-label Safety Run-in Phase of the study who received surgery. Results will be presented as treatment group "CNTO 2476  $3.0 \times 10^5$  cells".

# 2.6. Definition of Subgroups

Not applicable.

## 3. INTERIM ANALYSIS AND DATA MONITORING COMMITTEE REVIEW

A DSMB will be established to monitor data on an ongoing basis to ensure the continuing safety of the subjects enrolled in this study. The DSMB will consist of at least 1 medical expert in the relevant therapeutic area, and at least 1 statistician. The committee will meet periodically to review interim data. After the review, the DSMB will make recommendations regarding the continuation of the study.

The first formal safety data review will take place when 1-month safety follow-up data are available for the 21 subjects in the initial Safety Cohort. In addition, the DSMB charter will specify rules for interrupting the study enrollment in the event of device- or procedure-related safety events prior to the completion of the initial Safety Cohort. Events of special interest are choroidal hemorrhage, endophthalmitis or infections, retinal detachments, leakage of cells into the vitreous/need for vitrectomy, significant loss of vision defined as  $\geq 15$  letters lost compared to baseline (at the Week 4 post-surgery follow-up visit only), and failure to deliver cells/device failure.

Since no additional subjects are to be enrolled as of Protocol Amendment 3, there will be no further DSMB meetings and DSMB will be disbanded. Janssen retains the option to reform the DSMB should the need arise.

The DSMB's responsibilities, authorities, and procedures, will be documented in a separate charter.

The statistical analyses planned for the DSMB are provided in a separate DSMB SAP.

### 4. SUBJECT INFORMATION

### 4.1. Demographics and Baseline Characteristics

The following characteristics will be summarized: age (both as a continuous variable and with frequency counts for the following age groups: <65,  $\geq 65$  to <75,  $\geq 75$  years), sex, race, ethnicity, baseline weight, baseline height, baseline body mass index (BMI), tobacco substance usage; and the following baseline characteristics for both the treated and fellow eye: axial length, BCVA logMAR score, BCVA total letters correct, optical coherence tomography (OCT) central subfield thickness (CST) in microns ( $\mu$ ), total area of GA by fundus autofluorescence (FAF) in mm^2, and square root of total area of GA by FAF in mm.

Demographics and baseline characteristics for individual subjects will be presented in a data listing.

### 4.2. Medical History

General Medical History and Ocular Medical History will be summarized. The number and percentage of subjects with abnormalities recorded in the general medical history will be

tabulated by system organ class (SOC) and preferred term (PT). The number and percentage of subjects with ophthalmic disorders recorded in ocular medical history (which includes both past and ongoing) will be tabulated by SOC, PT and eye (treated, fellow, or both).

General Medical History and Ocular Medical History for individual subjects will be presented in data listings.

## 4.3. Disposition Information

The number of subjects will be tabulated for the following disposition categories: received openlabel surgery, completed 6 months of follow-up, discontinued prior to month 6, completed 12 months of follow-up, discontinued prior to month 12, completed total study follow-up, and discontinued after month 12 prior to end of study. Reasons for discontinuation will also be tabulated for subjects who discontinue prior to month 6, prior to month 12 or prior to end of study.

Subject disposition information for individual subjects will be presented in a data listing.

## 4.4. Treatment Compliance

Not applicable for this study as the investigational product will be administered subretinally as a single dose by the retinal surgeon. The administration of the investigational product will take place in an operating room using the Delivery System. Compliance will not require any activity by the subject.

## 4.5. Extent of Exposure

The number of subjects who received cells (investigational product [IP] was delivered to the subretinal space) will be tabulated as part of the Summary of Surgery and Delivery System.

## 4.6. Protocol Deviations

All Major Protocol Deviations will be documented in the study database.

The number of subjects with major protocol deviations during the study will be summarized by category. Subjects with more than one deviation will be counted in all applicable categories.

Major protocol deviations for individual subjects will be presented in a data listing.

## 4.7. Prior and Concomitant Medications

Prior and concomitant medications will be coded using the WHO Drug dictionary. Medication stopped prior to the Surgery Date will be considered as prior. Medications that are not considered prior, i.e., taken on or after the Surgery Date, will be considered concomitant medications. Missing or incomplete medications' start and end dates will be handled as described in Attachment 1 in order to determine whether the medications are concomitant or not.

Prior and concomitant ocular medications will be tabulated by medication class and standardized medication name. Prior and concomitant non-ocular medications will be tabulated separately. A

subject taking the same prior/concomitant medication multiple times will only be counted once for that prior/concomitant medication.

Prior and concomitant ocular and non-ocular medications for individual subjects will be presented in a data listing.

## 5. SAFETY

The verbatim terms used in the eCRF by investigators to identify adverse events (AEs) will be coded using the Medical Dictionary for Regulatory Activities (MedDRA). All reported AEs with onset from the surgery start date and onwards (i.e., treatment-emergent (TE) AEs, and AEs that have worsened since baseline) will be included in the analysis. Note that after Month 12, only serious AEs and ocular AEs are collected as per protocol. Missing or incomplete AE onset dates will be handled as described in Attachment 1.

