b) Only SAEs, ophthalmologic AEs, ongoing AEs from acute phase or any AEs designated as related to treatment or surgical procedure are recorded.

ABBREVIATIONS

ABCA4	ATP-binding cassettes A4
AE	adverse event
AMD	age-related macular degeneration
AMD-GA	age-related macular degeneration with geographic atrophy
AREDS	Age Related Eye Disease Study
ALT	alanine aminotransferase
AST	aspartate aminotransferase
BCVA	best corrected visual acuity
BSS	balanced salt solution
CFR	Code of Federal Regulations
CGIC	Clinician Global Impression of Change
CPS	critical print size
CRO	Contract Research Organization
DA	disc area
DARC	Digital Angiography Reading Center
DSMB	Data and Safety Monitoring Board
eCRF	electronic case report form
eDC	electronic data capture
ETDRS	Early Treatment Diabetic Retinopathy Study
FDA	Food and Drug Administration
FRI	Functional Reading Index questionnaire
GA	geographic atrophy
GCP	Good Clinical Practice
GTP	Good Tissue Practice
HIV	human immunodeficiency virus
hUTC	human umbilical tissue-derived cells
ICF	informed consent form
ICH	International Conference on Harmonisation
IEC	Independent Ethics Committee
IOP	intraocular pressure
IRB	Institutional Review Board
ITT	intent-to-treat
IWRS	interactive web response system
LASIK	laser-assisted in situ keratomileusis
LL BCVA	low luminance best corrected visual acuity
LLD	low luminance difference
logMAR	log of the minimum angle of resolution
MAIA2	Macular Integrity Assessment
MCID	minimal clinical important difference
MDS	microcatheter delivery system
MedDRA	Medical Dictionary for Regulatory Activities
mITT	modified intent-to-treat
MN Read	Minnesota reading test
MertK	Mer tyrosine kinase
MPS	Macular Photocoagulation Study
NEI-VFQ-25	National Eye Institute Visual Function Questionnaire
NOAEL	no-observed-adverse-effect level
PGIC-Q	Patient Clinician Global Impression of Change – Quality of Life
PGIC-S	Patient Clinician Global Impression of Change – Symptoms
PQC	Product Quality Complaint
PRO	patient-reported outcome(s)
pUTC	pig umbilical tissue-derived cells
RA	reading acuity
RCS	Royal College of Surgeons
RGC	retinal ganglion cell

RK	Radial keratotomy
ROS	rod outer segments
RPE	retinal pigment epithelium
RS	reading speed
SAE	serious adverse event
SAP	statistical analysis plan
SD-OCT	spectral domain optical coherence tomography
SF-36	Short Form (36) Health Survey
TEAE	treatment-emergent adverse event
ULN	upper limit of normal
US	United States
VEGF	vascular endothelial growth factor

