3.2. Study Design Rationale

This protocol amendment represents a significant reduction in the scope and duration of the planned trial, based on the sponsor's decision to discontinue the palucorcel development program. The intent of the current study design is to ensure adequate long-term safety follow-up of the subjects previously enrolled, while minimizing the visit burden on subjects and investigators.

The target population for this study is adult subjects (at least 55 years of age and no older than 90 years) with GA of the retina secondary to age related macular degeneration, with a baseline visual acuity of approximately logMAR 0.6 (20/80) to logMAR 1.6 (20/800). The best visual acuity of logMAR 0.6 (20/80) was selected because in this range, vision is compromised to a degree that restricts certain activities of daily living, and the potential benefit to the subjects justifies risks associated with the procedure and treatment.

A critical requirement of the program is the ability to deliver viable cells safely and efficiently to the subretinal space, without damaging the retina, and without leakage of cells into the vitreous. Currently, there is no alternative to surgical delivery. Previous studies using a transvitreal approach or an ab externo surgical approach have led to an unacceptable rate of retinal tears and detachments. The new suprachoroidal surgical procedure was selected and the new Delivery System designed with the goal of simplifying the procedure and facilitating the safe targeted delivery of CNTO 2476.

The use of the Delivery System in the Safety Cohort is a first-in-man study and AEs and device quality will be assessed by an independent DSMB after the first 21 subjects have been treated (or sooner, if a stopping threshold is reached).

Dose Selection

The breadth of the dose range is constrained by the cell density during cryopreservation and the minimal volumes that can be accurately administered to minimize the detachment at the subretinal injection site; the feasible doses were all studied in the Phase 1/2a study. The greatest experience to date is with the 3.0×10^5 cell dose (15 subjects). Although that dose was administered in a 27 μ L volume in the prior study, there is no reason to believe that the volume

of administration is relevant to either safety or efficacy; the AE profile for this dose/volume combination is comparable to a smaller dose (6.0×10^4 cells) given in a 50 μL volume.

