12.3. Procedures

12.3.1. All Adverse Events

All AEs and special reporting situations, whether serious or non-serious, will be reported from the time a signed and dated ICF is obtained until completion of the subject's last study-related procedure (which may include contact for follow-up of safety). Serious AEs, including those spontaneously reported to the investigator within 30 days after the last dose of CNTO 2476, must be reported using the Serious Adverse Event Form. The sponsor will evaluate any safety information that is spontaneously reported by an investigator beyond the time frame specified in the protocol.

All events that meet the definition of an SAE will be reported as SAEs, regardless of whether they are protocol-specific assessments. Anticipated events will be recorded and reported as described in [Attachment 1](#).

All AEs, regardless of seriousness, severity, or presumed relationship to treatment, must be recorded using medical terminology in the source document and the eCRF. Whenever possible, diagnoses should be given when signs and symptoms are due to a common etiology (eg, cough, runny nose, sneezing, sore throat, and head congestion should be reported as "upper respiratory infection"). Investigators must record in the eCRF their opinion concerning the relationship of the AE to study therapy. All measures required for AE management must be recorded in the source document and reported according to sponsor instructions.

The sponsor assumes responsibility for appropriate reporting of AEs to the regulatory authorities. The sponsor will also report to the investigator (and the head of the investigational institute where required) all suspected unexpected serious adverse reactions (SUSARS). The investigator (or sponsor where required) must report SUSARS to the appropriate Independent Ethics Committee/Institutional Review Board (IEC/IRB) that approved the protocol unless otherwise required and documented by the IEC/IRB.

For all studies with an outpatient phase, including Open-label studies, the subject must be provided with a "wallet (study) card" and instructed to carry this card with them for the duration of the study indicating the following:

- Study number
- Statement, in the local language(s), that the subject is participating in a clinical study
- Investigator's name and 24-hour contact telephone number
- Local sponsor's name and 24-hour contact telephone number (for medical staff only)
- Site number
- Subject number

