The study will consist of a 12-month acute phase, followed by a 2-year maximum duration follow-up period (3 years total) for all subjects.

The DSMB will monitor study data on an ongoing basis to ensure the continuing safety of the subjects enrolled in this study. The committee will meet periodically to review interim study data. After the review, the DSMB will make recommendations regarding the safety and continuation of the study.

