## 5.2. All AEs

The number and percentage of subjects who experienced at least 1 TE AE will be presented in summary tables by SOC and preferred term according to MedDRA terminology.

Serious TE AEs will be summarized and presented in a data listing.

Individual subject non-ocular AEs will be presented in a data listing.

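### The SAP's note on AE collection after Month 12 matches neither protocol rule, and its uncut all-TEAE table mixes full with restricted collection of non-serious, non-ocular events

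*SAP*

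**What the plan says.** Three places in the current text describe which AEs are captured in long-term follow-up.

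- SAP 5 (Safety) gives the narrowest description and attributes it to the protocol: "Note that after Month 12, only serious AEs and ocular AEs are collected as per protocol".
- Protocol Table 2 (long-term follow-up schedule), footnote b, is wider: "Only SAEs, ophthalmologic AEs, ongoing AEs from acute phase or any AEs designated as related to treatment or surgical procedure are recorded".
- Protocol 12.3.1 has no restriction after Month 12: "All AEs and special reporting situations, whether serious or non-serious, will be reported from the time a signed and dated ICF is obtained", and this runs "until completion of the subject's last study-related procedure". The same section adds: "All AEs, regardless of seriousness, severity, or presumed relationship to treatment, must be recorded". Protocol 9.5.1 likewise has AEs reported throughout the study, and Protocol 12.1.1 points to 12.3.1 for when AE recording ends.

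On length of follow-up, SAP 1.2 says: "The study will consist of a 12-month acute phase, followed by a 2-year maximum duration", which makes 3 years in total.

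On analysis, SAP 5 takes in all AEs with onset from surgery and sets no end date. SAP 5.2 then plans one table: "The number and percentage of subjects who experienced at least 1 TE AE will be presented in summary tables by SOC" and preferred term. It has no cut at Month 12 and no adjustment for follow-up time. The only split by timing is in SAP 5.1, for ocular AEs at the Week 4 visit.

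**The concern.** The SAP cites the protocol for a rule that the protocol does not contain, and the protocol itself gives two rules. Whichever of these describes what was recorded, the all-TEAE table joins two periods that may have been ascertained differently and prints one percentage for them. A reader of the study report would naturally take that percentage as the risk over the whole study.

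This matters because Protocol 3.2, after Amendment 3, gives the intent of the remaining design as to "ensure adequate long-term safety follow-up of the subjects previously enrolled". If a class of late events was never recorded, its absence from the table says nothing about whether such events occurred.

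**Working it through.** The plan states no figure to reproduce. The study is descriptive, and the documents give no AE rates for this cohort. The check is a comparison of the passages by type of event, followed by a count of the follow-up time affected.

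**Step 1. What each passage captures after Month 12**

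| Event | SAP 5 note | Table 2 footnote b | Protocol 12.3.1 and 9.5.1 |
|---|---|---|---|
| Serious | yes | yes | yes |
| Ocular, non-serious | yes | yes | yes |
| New, non-serious, non-ocular, related to treatment or surgical procedure | no | yes | yes |
| New, non-serious, non-ocular, judged unrelated | no | no | yes |
| Began before Month 12 and still ongoing | only if serious or ocular | yes | yes |

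Three results follow.

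1. The SAP note differs from both protocol rules, so it is inaccurate whichever of them governs.
2. The two protocol rules conflict in one row only: new, non-serious, non-ocular events judged unrelated.
3. The last row does not change incidence. An AE that began before Month 12 is already counted by its onset, so leaving it out of the SAP note removes no subject from the table.

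**Step 2. Follow-up time affected**

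- Planned follow-up: 12 + 24 = 36 months.
- Share after Month 12: 24/36 = 66.7%.
- With 21 subjects all followed to the end: 21 × 2 = 42 of 21 × 3 = 63 person-years.

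This is the share of time under the disputed rule. It is not the share of events affected.

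**Step 3. Which outputs are affected**

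- *SAP 5.2 all-TEAE table:* affected in its non-serious, non-ocular part. Up to Month 12 all AEs are collected. After that, collection is restricted (SAP note or footnote b) or complete (12.3.1), and the documents do not settle which.
- *SAP 5.1 ocular and serious ocular tables, and the SAP 5.2 serious TEAE summary:* not affected, because all three texts capture these events for 36 months.
- *SAP 5.3 events of special interest:* essentially unaffected. They use treated-eye AEs, surgery and procedure items from the eCRF, and BCVA at Week 4.

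**Step 4. What a cut would do**

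The three texts agree up to Month 12. A table of TEAEs with onset from surgery to Month 12 therefore has the same meaning under any of them.

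**The case against.** The strongest reply is that the protocol, not the SAP, binds the sites (Protocol 16.2.1), and that the SAP only describes analyses for the final report (SAP 1). On this view the SAP note is a loose summary that changes no data. It already tells the reader that collection narrows after Month 12. AE listings by subject are planned, and Study Day is defined for AE onset, so with 21 subjects in one group any late event that was recorded can be found. There is no comparison between arms to bias, and the outputs closest to the primary objective are sound.

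Most of this stands, and it limits the point. It does not repair the table: a listing shows only what was recorded, and the disclosure in the SAP is itself wrong about what the protocol asks for.

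Three stronger readings are tempting but not supported.

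- *A reader might infer that sites would drop late AEs related to the cells or the surgery.* Both protocol rules require those AEs to be recorded, so a site following either one keeps them. Only the SAP note leaves them out.
- *A reader might infer that sites did follow different rules.* The conflict makes this possible, but nothing shows that it happened. Protocol 17.6 provides shared eCRF completion guidelines and sponsor review.
- *A reader might try to size the understatement.* Assume a constant hazard and a 12-month risk of 20% for non-serious, non-ocular AEs. The 36-month risk is then 1 − (1 − 0.20)^3 = 48.8%, against 20% if nothing is captured after Month 12. But neither protocol rule prescribes zero capture. Under footnote b, with an assumed share r of such AEs judged related, the figure is 1 − 0.80^(1 + 2r): 23.5%, 28.4% or 36.0% for r = 10%, 25% or 50%. Under 12.3.1 there is no shortfall. The 20%, the values of r and the constant hazard are all assumptions. Protocol 3.1 expects most procedure-related AEs to show within hours of surgery, which argues against a constant hazard for those events. These figures are not an estimate for this trial.

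**Conclusion.** The SAP sentence is wrong as written: it credits the protocol with a rule found in neither protocol passage. The protocol passages also need reconciling with each other, for the single class of event on which they differ.

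The consequence for analysis is confined to the non-serious, non-ocular part of the SAP 5.2 all-TEAE table. There, one percentage spans a fully collected period and a longer period (24 of 36 months) whose collection is restricted or undefined, so it cannot be read as a risk over either 12 or 36 months. If collection was restricted, the table would tend to understate such events over the whole study. By how much cannot be computed from the documents.

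This conclusion rests on the current wording alone, and on the SAP planning no other cut or follow-up adjustment for that table. It makes no claim about what the eCRF in fact captured.

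**What to change.** 1. Reconcile Protocol Table 2 footnote b, Protocol 9.5.1, Protocol 12.3.1 and SAP 5 into one recording rule for the period after Month 12. The documents do not say which protocol passage takes precedence, so the sponsor has to settle it.
2. Correct the SAP 5 sentence to match that rule, and state which AE categories the eCRF captured after Month 12.
3. Present the SAP 5.2 all-TEAE table for onset from surgery to Month 12.
4. Add one table of AEs with new onset after Month 12, limited to the categories collected and labelled as such. AEs ongoing from the acute phase should not be counted again in it.

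The ocular, serious and special-interest tables need no split. The cost is a few sentences and one extra descriptive table.
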